### **Time to Grade 3-5 AE**

Additional exploratory analysis may be performed on the time to the first Grade 3-5 AE. The time to the first Grade 3-5 AE is defined as the time from the first day of study drug to the first event of a Grade 3-5 AE. Summary statistics will be provided.

### 3.6.3 Statistical Methods for Patient-Reported Outcome Analyses

This section describes the planned analyses for the PRO endpoints.

#### 3.6.3.1 PRO Scoring Algorithm

EORTC QLQ-C30 Scoring: Each scale or item is scored between 0 and 100, according to the EORTC QLQ-C30 standard scoring algorithm [Scott, N. W., et al 2008]. For global health status/quality of life and all functional scales, a higher value indicates a better level of function; for symptom scales and items, a higher value indicates increased severity of symptoms.

EORTC QLQ-CR29 Scoring: All of the scales and single-item measures range in score from 0 to 100. A high score for the functional scale and functional single-items represents a high level of functioning, whereas a high score for the symptom scales and symptom single-items represents a high level of symptomatology or problems.

#### 3.6.3.2 PRO Completion and Compliance Summary

Completion and compliance of EORTC QLQ-C30 and CCI by visit and by treatment will be described. Numbers and percentages of complete and missing data at each visit will be summarized.

Completion rate of treated participants (CR-T) at a specific visit for a given instrument is defined as the number of treated participants who complete at least one item on that PRO instrument over the number of treated participants in the PRO analysis population.

$$\text{CR-T} = \frac{\text{Number of treated participants who complete at least one item}}{\text{Number of treated participants in the PRO analysis population}}$$

The completion rate is expected to decrease at later visits during study period for reasons such as study design (e.g., PROs not required following progression), patient discontinuation, etc. Therefore, the compliance rate (CR-E) will also be presented in addition to completion rate. CR-E is defined as the number of treated participants who complete at least one item of the instrument over number of participants who are expected to complete the PRO assessment at that visit, excluding participants missing by design such as death, discontinuation, translation not available.

$$\text{CR-E} = \frac{\text{Number of treated participants who complete at least one item}}{\text{Number of treated participants who are expected to complete}}$$

The completion and compliance status will be summarized as below:

- Completed as scheduled
- Not completed as scheduled
- Off-study: not scheduled to be completed.

The reasons for non-completion as scheduled of these measures are collected using “miss\_mode” forms filled by site personnel and will be summarized in a table format. The schedule (study visits and estimated study times) and mapping of study visit to analysis visit for PRO data collection is provided in [Table 5](#).

Table 5 PRO Data Collection Schedule and Mapping of Study Visit to Analysis Visit

Treatment Week	Week 0	Week 4	Week 8	Week 12	Week 24	Week 36
Day	1	29	57	85	169	253
Range (relative day to first dose date)	[-7, 7]	[8, 42]	[43, 70]	[71, 126]	[127, 210]	[211, 294]
Treatment Week	Week 48	Week 60	Week 72	Week 84	Week 96	
Day	337	421	505	589	673	
Range (relative day to first dose date)	[295, 378]	[379, 462]	[463, 546]	[547, 630]	[631, 714]	

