### **3.4.3 PRO Endpoints**

- Change from baseline in EORTC QLQ-C30 global health status/quality of life scores (QoL), physical functioning and appetite loss and EORTC QLQ-CR29 bloating scores for MK-4280A versus standard of care
- Time to confirmed deterioration (TTD) in EORTC QLQ-C30 global health status/QoL, physical functioning and appetite loss and EORTC QLQ-CR29 bloating scores for MK-4280A versus standard of care

Based on prior literature (Bjordal, et al., 2000; Osoba D, 1998 [Osoba, D., et al 1998]; King, 1996 [King, M. T. 1996]), a 10 points or greater worsening from baseline for each scale represents a clinically relevant deterioration for EORTC. TTD is defined as the time from baseline to the first onset of a 10 or more points deterioration from baseline with confirmation at the subsequent visit of a 10 or more points deterioration from baseline.

- **CCI**  
[REDACTED]
- Overall improvement / stability + improvement in EORTC QLQ-C30 global health status / QoL, physical functioning and appetite loss and EORTC QLQ-CR29 bloating scores:

The assessment for possible PRO response at a time point considering subsequent confirmation is defined as follows:

Assessment Category at a time point (one analysis visit)	Change from baseline at a time point (one analysis visit)	Change from baseline at the subsequent time point (the next consecutive analysis visit)
Improvement	score improved from baseline by $\geq 10$ points	score improved from baseline by $\geq 10$ points
Stability	score improved from baseline by $\geq 10$ points	score improved or worsened from baseline by $< 10$ points
	score improved or worsened from baseline by $< 10$ points	score improved or worsened from baseline by $< 10$ points
	score improved or worsened from baseline by $< 10$ points	score improved from baseline by $\geq 10$ points
Worsening	score worsened from baseline by $\geq 10$ points	not required
Unconfirmed	A time point assessment that doesn't meet any of the above criteria.	

The overall improvement is defined as the best observed PRO response that is an improvement among all post-baseline assessments by timepoint. The overall improvement + stability is defined as the best observed PRO response that is an improvement or stability among all post-baseline assessments by timepoint.

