### **3.5.3 PRO Analysis Populations**

The PRO analyses are based on the PRO FAS population, defined as all randomized participants who have at least one PRO assessment available for the specific endpoint and have received at least one dose of the study intervention. Participants will be analyzed in the treatment group to which they are randomized.

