### **3.6.3.4 Time to Confirmed Deterioration (TTD)**

The Kaplan-Meier method will be used to estimate the TTD curve for each treatment group. The estimate of median time-to-deterioration and its 95% confidence interval will be obtained from the Kaplan-Meier estimates. The treatment difference in TTD will be assessed by the stratified log-rank test. A stratified Cox proportional hazard model with Efron's method of tie handling and with a single treatment covariate will be used to assess the magnitude of the treatment difference (ie, HR). The HR and its 95% CI will be reported. The stratification factors used for randomization (Section 6.3.2 of the protocol) will be used as the stratification factors in both the stratified log-rank test and the stratified Cox model.

The approach for the TTD analysis will be based on the assumption of non-informative censoring. The participants who do not have deterioration on the last date of evaluation will be censored. [Table 6](#) provides censoring rule for TTD analysis.

Table 6 Censoring Rules for Time to Confirmed Deterioration

Scenario	Outcome
Deterioration documented	Event observed at time of assessment (first deterioration)
Ongoing or discontinued from study without deterioration	Right censored at time of last assessment
No baseline assessments	Right censored at treatment start date

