## 4.2 Technical Details for cLDA Model

The cLDA model assumes a common mean across treatment groups at baseline and a different mean for each treatment at each of the post-baseline time points. In this model, the response vector consists of baseline and the values observed at each post-baseline time point. Time is treated as a categorical variable so that no restriction is imposed on the trajectory of the means over time. The cLDA model is specified as follows:

$$E(Y_{ijt}) = \gamma_0 + \gamma_{jt}I(t > 0) + \beta X_i, j = 1, 2, 3, \dots, n; t = 0, 1, 2, 3, \dots, k$$

where  $Y_{ijt}$  is the PRO score for participant  $i$ , with treatment assignment  $j$  at visit  $t$ ;  $\gamma_0$  is the baseline mean for all treatment groups,  $\gamma_{jt}$  is the mean change from baseline for treatment group  $j$  at time  $t$ ;  $X_i$  is the stratification factor (binary) vector for this participant, and  $\beta$  is the coefficient vector for stratification factors. An unstructured covariance matrix will be used to model the correlation among repeated measurements. If the unstructured covariance model fails to converge with the default algorithm, then Fisher scoring algorithm or other appropriate methods can be used to provide initial values of the covariance parameters. In the rare event that none of the above methods yield convergence, a structured covariance such as Toeplitz can be used to model the correlation among repeated measurements. In this case, the asymptotically unbiased sandwich variance estimator will be used. The cLDA model implicitly treats missing data as missing at random (MAR).

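### Table 5 lets a PRO completed up to Day 7 count as Week 0, so a score taken after the first dose can become the PRO baseline

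*SAP*

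**What the plan says.** - **Visit windows.** Section 3.6.3.2 says that the "mapping of study visit to analysis visit for PRO data collection is provided in" Table 5. The first columns of its range row read "Range (relative day to first dose date) [-7, 7] [8, 42"]. Week 0 has nominal Day 1 and covers Day -7 to Day 7; Week 4 has nominal Day 29 and starts at Day 8.
- **Use of baseline.** Section 3.4.3: "TTD is defined as the time from baseline to the first onset of a 10 or more points deterioration from baseline"; the next visit must confirm it. The improvement and stability categories in the same section rest on "Change from baseline at a time point (one analysis visit") and the same 10-point cut-off. Section 3.6.3.3 analyses change from baseline with a cLDA model.
- **Model.** Section 4.2: "The cLDA model assumes a common mean across treatment groups at baseline and a different mean for each treatment at each of the post-baseline time". Baseline is visit t = 0.
- **Missing baseline.** Section 3.6.3.4, Table 6, for a participant without any baseline assessment: "Right censored at treatment start date".
- **Population.** Section 3.5.3 admits "all randomized participants who have at least one PRO assessment available for the specific endpoint and have received at least one dose of the study". It does not ask for a pre-dose value.
- **Blinding.** Section 3.1 describes the study as open-label.

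The SAP has no separate definition of PRO baseline and no rule for choosing among several records in the Week 0 window.

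**The concern.** A window that runs a week either side of its target is ordinary for a follow-up visit. It is not suitable for the reference value, because the later half of the window lies on treatment. A participant who misses the Day 1 form and completes it on Day 5 has, by Table 5, a Week 0 score recorded after treatment began and with the allocation known.

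Three things follow:

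- An early change in appetite, function or global health is absorbed into the baseline instead of being measured as change. The two arms receive different drugs, so early shifts need not be equal and need not cancel. The arm with the larger early worsening then tends to look better at later visits.
- The common baseline mean in the cLDA model is justified by randomization only for values that treatment cannot have affected.
- A participant with no pre-dose form but one on Days 2 to 7 does not reach the no-baseline row of Table 6 and is analysed against an on-treatment reference.

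**Working it through.** The SAP states no figure for this point, so there is none to reproduce. The check has three parts.

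**1. What the windows allow.** The nominal days in Table 5 satisfy (day - 1)/7 = week: Day 1 is Week 0 and Day 29 is Week 4. Day 1 is therefore the day of first dose. The windows are contiguous and each nominal day lies inside its own window. Within Week 0, Days 2 to 7 fall after the first dose, and Day 7 is 7 - 1 = 6 days after it.

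**2. Effect on one participant's thresholds.** Take a functional scale and let B be the true pre-dose score. Suppose the participant has fallen 10 points when the late baseline is taken, so the recorded baseline is B - 10.

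- Deterioration should be reached at B - 10. It is now reached at (B - 10) - 10 = B - 20, a 20-point fall from the true starting value.
- Improvement should be reached at B + 10. It is now reached at (B - 10) + 10 = B, so a mere return to the pre-dose level counts as improved.

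In general both thresholds move by the full early change. An early improvement moves them the other way.

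**3. Effect on the estimated treatment difference.** With two visits, equal variances and a common baseline mean, the cLDA estimate is the difference in follow-up means minus rho times the difference in observed baseline means. Let f be the share of late baselines, d the between-arm difference in first-week shift and rho the correlation between baseline and follow-up. The observed baselines then differ on average by f x d, so

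- bias of the cLDA difference = -rho x f x d
- bias of a raw mean-change difference = -f x d

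f, d and rho are assumptions; the SAP gives none of them. Magnitudes in points:

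| f | d | cLDA, rho 0.5 | cLDA, rho 0.4 to 0.6 | Raw change |
|---|---|---|---|---|
| 5% | 5 | 0.125 | 0.10 to 0.15 | 0.25 |
| 5% | 10 | 0.25 | 0.20 to 0.30 | 0.50 |
| 10% | 5 | 0.25 | 0.20 to 0.30 | 0.50 |
| 10% | 10 | 0.50 | 0.40 to 0.60 | 1.00 |

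The raw-change column applies to the empirical mean-change plots in Section 3.6.3.3.

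For scale, take 432/2 = 216 per arm, an assumed SD of 22 and rho 0.5. The standard error is 22 x sqrt(1 - 0.25) x sqrt(2/216) = 1.83. The cLDA bias at rho 0.5 is then 0.125/1.83 = 0.07 to 0.50/1.83 = 0.27 of a standard error. With incomplete follow-up the standard error is larger and the ratio smaller.

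The formula was checked by a large simulation with no true difference, at a deliberately high f of 30%, d = -10 and rho 0.5. It gave a spurious difference of 1.48 for the cLDA (formula 1.50) and 3.03 for raw change (formula 3.00). That run tests the algebra and is not a forecast for this trial.

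**The case against.** The strongest reply is that Table 5 sits in a section on completion and compliance, says Week 0 and never says baseline. The protocol, which is not at hand, may require questionnaires before dosing on Day 1. Late forms would then be deviations, the window only a tolerance, and the effect small.

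Part of this stands. Reading Week 0 as baseline is an inference. It is a firm one, because Week 0 is the only visit before Week 4 and Section 4.2 places baseline at t = 0. If nearly all forms are completed before dosing, the average effect is indeed small. But a rule on when forms are completed does not say how a late form is classified in the analysis. Table 5 does say so, and it classifies the form as Week 0.

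A reader might also infer more than the SAP supports:

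- **That Table 5 contradicts Section 4.2.** It does not. Section 4.2 states a modelling assumption. Late baselines make it approximate for the participants concerned, and the treatment comparison is biased only if early shifts, or the share of late baselines, differ between arms.
- **That the bias could be large.** A share of 30% with a 10-point difference gives 0.5 x 0.30 x 10 = 1.5 points, but nothing in the SAP points to either value. A share of that size would also make the remedy costly, since about as many participants would lose their baseline.

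**Conclusion.** The point holds as a weakness in a stated analysis rule. Followed as written, Table 5 permits a PRO baseline taken up to 6 days after first dose in an open-label trial, and no other text in the SAP prevents it.

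Its likely size for the mean comparison is small: about 0.1 to 0.5 point under the assumed 5-10% late baselines, 5-10 point between-arm difference in first-week shift and correlation of 0.5. For confirmed deterioration and improvement/stability, an affected participant's threshold shifts by the full early change; how many participants that concerns cannot be known from the SAP.

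The PRO endpoints are outside the alpha-controlled hypotheses in Section 3.8, so conclusions on OS, PFS and ORR do not change. The case for acting is that the rule is easily corrected and is better settled before the PRO data are analysed.

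**What to change.** - In Table 5, close the Week 0 window at the first dose: [-7, 1].
- Add a sentence defining the PRO baseline as the last assessment on or before Day 1 and before the first dose. This also settles which record is used when several fall in the window.
- Leave Day 2 to 7 records out of the visit-based analyses. They should not be moved to Week 4: a Day 2 form would then stand for a visit with nominal Day 29, 27 days later.
- Participants without a pre-dose PRO follow the existing TTD rule ("No baseline assessments Right censored at treatment start date") and enter the cLDA with post-baseline values only. The model carries baseline in the response vector and treats missing values as missing at random, so it needs no change.
- State how these participants are counted in the improvement and stability rates, unless the redacted Table 7 already does so.
- As a sensitivity analysis, repeat the PRO analyses with the [-7, 7] window to show whether the choice matters.

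The cost is one table cell and a few sentences. Some participants, probably few, lose a baseline value and so do not contribute to TTD or improvement/stability. No sample size, power or alpha figure changes, and this source of bias is removed (f = 0).

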### **3.6.3.3 Change from Baseline**

The time point for the change from baseline analysis is defined as the latest time point at which  $CR-T \geq 60\%$  and  $CR-E \geq 80\%$ , and week 8 based on blinded data review prior to the database lock for any PRO analysis.

To assess the treatment effects on the PRO score change from baseline in the global health status/QoL, physical, appetite loss, bloating, and ~~CCI~~ [REDACTED], a constrained longitudinal data analysis (cLDA) model proposed by Liang and Zeger [Liang, K.-Y. and Zeger, S. L. 2000] will be applied, with the PRO score as the response variable, and treatment, time, the treatment by time interaction, and the stratification factors used for randomization (Section 6.3.2 of the protocol) as covariates. The treatment difference in terms of least square mean change from baseline will be estimated from this model together with 95% CI. Model-based least square mean with 95% CI will be provided by treatment group for PRO scores at baseline and post-baseline time point.

The technical details on the cLDA model are in the appendix of this sSAP.

Line plots for the empirical mean change from baseline in EORTC QLQ-C30 global health status/QoL, physical, appetite loss and bloating score will be provided across all time points as a supportive analysis.

In addition, the model-based LS mean change from baseline to the specified post-baseline time point together with 95% CI will be plotted in bar charts for EORTC QLQ-C30 global health status/QoL scores, all functioning and symptom scores, and for EORTC QLQ-CR29 all functioning and symptom scores.

### **3.6.3.4 Time to Confirmed Deterioration (TTD)**

The Kaplan-Meier method will be used to estimate the TTD curve for each treatment group. The estimate of median time-to-deterioration and its 95% confidence interval will be obtained from the Kaplan-Meier estimates. The treatment difference in TTD will be assessed by the stratified log-rank test. A stratified Cox proportional hazard model with Efron's method of tie handling and with a single treatment covariate will be used to assess the magnitude of the treatment difference (ie, HR). The HR and its 95% CI will be reported. The stratification factors used for randomization (Section 6.3.2 of the protocol) will be used as the stratification factors in both the stratified log-rank test and the stratified Cox model.

The approach for the TTD analysis will be based on the assumption of non-informative censoring. The participants who do not have deterioration on the last date of evaluation will be censored. [Table 6](#) provides censoring rule for TTD analysis.

Table 6 Censoring Rules for Time to Confirmed Deterioration

Scenario	Outcome
Deterioration documented	Event observed at time of assessment (first deterioration)
Ongoing or discontinued from study without deterioration	Right censored at time of last assessment
No baseline assessments	Right censored at treatment start date

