Multiplicity	The overall type I error over the primary and secondary hypotheses is strongly controlled at 2.5% (1-sided), CCI [REDACTED] By using the graphical approach of Maurer and Bretz [Maurer, W. and Bretz, F. 2013], if one hypothesis is rejected, the alpha will be shifted to other hypotheses.
Sample Size and Power	CCI [REDACTED]
Abbreviations: APaT = all participants as treated; BICR = blinded independent central review; CI = confidence interval; DMC = data monitoring committee; eDMC = external data monitoring committee; FAS = full-analysis set; HR = hazard ratio; ITT = intent to treat; M&N = Miettinen and Nurminen; ORR = objective response rate; CCI [REDACTED]; PFS = progression free survival; SOC = standard of care	

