### 3.9 Sample Size and Power Calculations

The study will randomize 432 participants in a 1:1 ratio into the MK-4280A arm (Arm A) and the standard of care arm (Arm B). OS is the primary endpoint for the study, with PFS and ORR as the key secondary endpoints.

For the OS endpoint, based on a target number of 386 events and 1 IA at approximately 80% of the target number of events, the study has approximately 93.5% power to detect a HR of 0.7 at the initially allocated  $\alpha=0.025$  (1-sided).

For the PFS endpoint, based on a target number of 419 events at the IA (final PFS analysis), the study has approximately 99% power to detect a HR of 0.65 at the reallocated  $\alpha=0.0125$  (1-sided) if only OS hypothesis is rejected.

Based on the 432 participants with at least approximately 10 months of follow-up, the power of the ORR testing at the reallocated  $\alpha=0.0125$  (1-sided) if only OS hypothesis rejected is approximately 97% to detect a 10-percentage point difference between an underlying 2% ORR in the control arm (Arm B) and a 12% ORR in the experimental arm (Arm A).

Note that the above OS and PFS power calculations are based on a constant HR assumption.

[figure not shown]
Based on CORRECT, RE COURSE, and SUNLIGHT studies (Section 4.2.1.1 of protocol), the above sample size and power calculations for OS and PFS assume the following:

- OS follows an exponential distribution with a median of 7.5 months for the control group.
- PFS follows an exponential distribution with a median of 2 months for the control group.
- Enrollment period of 12 months with enrollment ramp-up over first 2 months.
- An annual dropout rate of 2% and 5% for OS and PFS, respectively
- A follow-up period of 22 and 10 months and for OS and PFS, respectively, after the last participant is randomized.

The sample size and power calculations were performed using R (“gsDesign” package).

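### Time to deterioration censors death and reports only Kaplan-Meier curves and medians, which overstate the probability of deteriorating before death; cumulative incidence should stand beside them

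*SAP*

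**What the plan says.** SAP Section 3.4.3 defines the endpoint: "TTD is defined as the time from baseline to the first onset of a 10 or more points deterioration from baseline", confirmed at the next visit. Death is not part of the event. It applies to four scales: global health status/QoL, physical functioning, appetite loss and bloating.

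Section 3.6.3.4 estimates the curve in each arm by Kaplan-Meier and adds: "The estimate of median time-to-deterioration and its 95% confidence interval will be obtained from the Kaplan-Meier estimates". Arms are compared by stratified log-rank test and stratified Cox model. On censoring it states: "The approach for the TTD analysis will be based on the assumption of non-informative censoring".

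Table 6 has three rows: deterioration documented; "Ongoing or discontinued from study without deterioration", which is right censored at the last assessment; and no baseline assessment. None names death. A participant who dies without a recorded deterioration can only fall in the second row. Section 3.6.3.2, by contrast, lists death separately from discontinuation when it explains why questionnaires are missing by design.

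The visible text contains no competing-risk analysis for TTD. Table 7, the strategy for the key PRO variables, is redacted.

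**The concern.** A participant who has died can no longer deteriorate, so death is a competing event and not an ordinary loss to follow-up. If it is treated as independent censoring, Kaplan-Meier estimates how many would deteriorate if nobody died. That is a legitimate hypothetical quantity, but it is not the proportion of participants who deteriorate, which is how such a curve is usually read.

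The distinction could be ignored if deaths were rare. They are not: "OS follows an exponential distribution with a median of 7.5 months for the control group". What is at stake is the absolute description of quality of life in each arm, meaning the curve, any percentage read from it, and the meaning of the median. No formal test depends on it.

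**Working it through.** **Inputs from the plan (SAP Section 3.9).** Control OS is exponential with median 7.5 months, so the death hazard is d = ln 2 / 7.5 = 0.0924 per month. The OS hazard ratio is 0.7, so in Arm A d = 0.0647 (median 10.7 months). With 432 participants randomised 1:1, there are 216 per arm.

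**Check of the design figure.** The plan says "the study has approximately 93.5% power to detect a HR of 0.7 at the initially allocated" alpha. With 309 and 386 events the expected Z values are 0.5 × √309 × 0.3567 = 3.13 and 0.5 × √386 × 0.3567 = 3.50. With bounds 2.2504 and 2.0249 and correlation √(309/386), a bivariate normal calculation gives power 93.5% and one-sided alpha 0.0250. This reproduces the plan's figure and confirms the hazard ratio. It does not test the 7.5-month median, which affects only timing.

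**Deaths at these assumptions.** Week 24 is day 168, or 5.52 months; Week 48 is day 336, or 11.04 months (30.44 days per month). 1 − exp(−d t) gives 40% (control) and 30% (Arm A) dead by Week 24, and 64% and 51% by Week 48.

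**Assumptions not in the plan.** The deterioration rate is not given. I take it as exponential with median m from 2 to 24 months, the same in both arms, independent of death, with questionnaires collected until death. Then b = ln 2 / m, and:

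- Kaplan-Meier limit: 1 − exp(−b t)
- Cumulative incidence with death competing: b/(b+d) × [1 − exp(−(b+d) t)]

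Example: m = 6, control, Week 24. b = 0.1155 and b + d = 0.2079. Kaplan-Meier: 1 − exp(−0.638) = 47.1%. Cumulative incidence: 0.556 × [1 − exp(−1.148)] = 37.9%. The gap is 9.2 points.

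Results in percent, with the gap in points in brackets (gaps come from unrounded values):

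| Assumed median | Week 24 KM, both arms | Control | Arm A | Week 48 KM, both arms | Control | Arm A |
|---|---|---|---|---|---|---|
| 2 months | 85.2 | 71.9 (13.3) | 75.6 (9.7) | 97.8 | 78.3 (19.5) | 83.4 (14.4) |
| 4 months | 61.6 | 50.2 (11.4) | 53.2 (8.3) | 85.2 | 61.7 (23.5) | 67.6 (17.7) |
| 6 months | 47.1 | 37.9 (9.2) | 40.4 (6.7) | 72.1 | 50.0 (22.1) | 55.3 (16.7) |
| 12 months | 27.3 | 21.7 (5.6) | 23.2 (4.1) | 47.1 | 31.1 (16.0) | 35.0 (12.2) |
| 24 months | 14.7 | 11.6 (3.1) | 12.4 (2.3) | 27.3 | 17.6 (9.7) | 19.9 (7.4) |

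The range is 2.3 to 13.3 points at Week 24 and 7.4 to 23.5 at Week 48. For m = 6 the Greenwood standard error of the Kaplan-Meier estimate is 3.9 (control) and 3.8 (Arm A) points at Week 24, and 4.2 and 3.8 at Week 48.

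**Median.** The time at which half the arm has deteriorated is −ln[1 − 0.5(b+d)/b] / (b+d). For m = 6 this is −ln(0.10)/0.2079 = 11.1 months in control and −ln(0.22)/0.1802 = 8.4 months in Arm A. The Kaplan-Meier median is 6.0 months in both. In control, 50% is never reached once m is 7.5 months or longer, because b/(b+d) is then at most 0.5.

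**Sensitivity to independence.** If the death hazard before deterioration is half the OS hazard (my assumption), the Week 24 gaps for m = 6 fall to 5.0 (control) and 3.6 (Arm A) points. For m = 12 they are 3.0 and 2.2, below one standard error (3.2).

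**Sensitivity to PRO follow-up.** Section 3.6.3.2 gives as an example "PROs not required following progression", and Section 3.9 assumes a control PFS median of 2 months. If questionnaires stop at progression and m = 6, the number of controls still at risk is 216 × exp[−(ln 2/6 + ln 2/2) t], about 17 at Week 24 and 1 at Week 48. The standard errors rise to about 6 and 12 points.

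**The case against.** The strongest reply is that the plan states its censoring assumption openly. Under it, Kaplan-Meier estimates a defined hypothetical quantity, and the log-rank test and Cox hazard ratio compare cause-specific hazards whether or not death is censored. TTD is also outside the tested hierarchy: "The overall type I error over the primary and secondary hypotheses is strongly controlled at 2.5% (1-sided"), and Section 3.8 gives alpha only to OS, PFS and ORR. All of this stands. It limits the point to the absolute figures.

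It is also fair that the size depends on a deterioration rate the plan does not give, that deaths concentrated after deterioration would shrink the gap, and that the plan schedules no TTD rate at Week 24 or Week 48. Those weeks only illustrate the curve. Table 7 is redacted, so a supportive competing-risk analysis cannot be ruled out. Table 6, however, is visible and is the stated censoring rule.

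Three stronger readings are tempting, and the SAP supports none of them.

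- A reader might infer that Kaplan-Meier medians set side by side mislead even when deterioration hazards are equal. The working shows the reverse: Kaplan-Meier gives 6.0 and 6.0 months, correctly showing no difference. The cumulative-incidence medians of 11.1 and 8.4 months make the longer-lived arm look worse.
- For the same reason, a reader might want the Kaplan-Meier median replaced. That would exchange one misreading for another.
- A reader might count progression as a competing event as well and reach much larger gaps. Progression may end observation, but it does not prevent deterioration. Section 3.4.3 does not define TTD as deterioration before progression, so such a figure compares two endpoints and is not a bias.

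**Conclusion.** The point holds for the absolute TTD figures. Death without deterioration is censored by implication, death is common at the plan's own OS assumptions, and one minus Kaplan-Meier therefore exceeds the actual probability of deteriorating before death. The direction does not depend on the deterioration rate. The size does: about 2 to 13 points at Week 24 and 7 to 24 points at Week 48, for an assumed deterioration median of 2 to 24 months, exponential times, independence from death and questionnaires until death. Under the first alternative above the gap is roughly halved; under the second, precision at those weeks is much lower.

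The between-arm test and hazard ratio are unaffected if read as cause-specific. The point deserves correction but does not touch the trial's confirmatory conclusions.

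**What to change.** In SAP Section 3.6.3.4 and Table 6:

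1. Give death without prior deterioration its own row in Table 6, so that its handling is stated and not inferred.
2. Beside the Kaplan-Meier output, add Aalen-Johansen cumulative incidence per arm of deterioration and of death without deterioration, with 95% confidence intervals. Use it for any statement about the proportion of participants who deteriorate.
3. Show the two cumulative incidences together, because lower mortality alone raises the cumulative incidence of deterioration in an arm.
4. Keep the Kaplan-Meier median, but label it as the hypothetical, death-censored quantity.
5. Keep the stratified log-rank test and Cox model, and label the hazard ratio cause-specific.
6. Keep the statement on non-informative censoring, and add that it is not expected to hold for death.

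The cost is SAP wording and a few lines of code; death dates are already needed for OS. The downside is one extra display per scale, and care in reading it.
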